5.4. Exploratory Endpoints

5.4.1. Definition

Formulae to be used for derived variables, including data conversions, are provided in the tables below. Note that for time to event variables the actual date times will be used.

5.4.1.1. Impact of Influenza (Flu-iiQ™ Modules 2, 3, 4)

Composite impact score	
Per datetime and per module (modules 2, 3 and 4) of the FLU-iiQ™ questionnaire a composite impact score will be calculated as the mean of the non-missing items in each module respectively on a 0-3 scale.
 
If more than 50% of the items to construct a Composite impact score are missing, then the value for that composite impact score for that individual and time point is coded as missing (ie, 4 or more items missing for module 2, 3 or more items missing for module 3, 3 or more items missing for module 4).

Composite impact score change from baseline	
For each module (modules 2, 3 and 4) of the Flu-iiQ™ questionnaire:
 
Composite impact score post-baseline value – composite impact score baseline value

Time to normalization of impact on daily activities (hours)	
Time to normalization of impact on daily activities is based on module 2 of the FLU-iiQ™ questionnaire, and is defined as the time in hours from the first dose of investigational product until the first one of a successive series of 3 recordings where all scores in the FLU-iiQ™ module are reported as “no difficulty”.
 
The 3 successive recordings may have been done over 4 scheduled successive analysis timepoints, in case of 1 missing in between timepoint.
 
Censoring will be done similar to the time to resolution of influenza symptoms.

Time to normalization of impact on emotions (hours)	
The algorithm for time to normalization of impact on emotions is similar to ‘Time to normalization of impact on daily activities’. Module 3: emotional impact is used and recordings should report “not at all” to define resolution.

Time to normalization of impact on others (hours)	
The algorithm for time to normalization of impact on others is similar to ‘Time to resumption of normalization of impact on daily activities’. Module 4: impact on others is used and recordings should report “not at all concerned” to define resolution.

5.4.2. Analysis Methods**5.4.2.1. Impact of Influenza (Flu-iiQ™ Modules 2, 3, 4)****Composite impact scores**

The actual composite impact scores and changes from baseline will be shown descriptively and by mean (SE) plots per analysis visit and timepoint.

Time to resumption of normal activities for usual activities, for emotional impact, for impact on others

The times to resumption of normal activities will be analyzed similarly as the time to resolution of the individual symptoms of influenza.

6. TASTE AND SWALLOWABILITY

6.1. Definition

Taste and swallowability will only be assessed for adolescents in this study.

The acceptability of the taste will be derived from the responses to the overall question on taste, dichotomizing the responses 'None' and 'Weak' as acceptable and responses 'Moderate' or 'Strong' as unacceptable.

For the swallowability, a dichotomization of the responses will be made of 'slightly difficult' or worse vs. 'neither difficult nor easy' or better.

6.2. Analysis Methods

Taste and swallowability questionnaire results will be summarized for the safety set per tablet intake (first and last intake of the study drug) by means of frequency tabulations of the actual responses. Additionally, the number of subjects (%) will be presented by response category (including dichotomization) for swallowability and taste separately.

7. SAFETY

All safety analyses will be done on the Safety Set.

7.1. Adverse Events

7.1.1. Definitions

Coding of AE

The verbatim terms used in the eCRF by investigators to identify AEs will be coded using the Medical Dictionary for Regulatory Activities. Events are looked at on the level of their preferred term.

Treatment-emergent AE

Pre-treatment AEs are defined as AEs that were reported or worsened after signing the ICF up to the start of study drug dosing. Treatment-emergent AEs (TEAE) are defined as AEs that were reported or worsened on or after the start of study drug dosing and up to and including the end of the follow-up phase.

An AE, at the preferred term level, is considered treatment-emergent if:

- An AE starts after or at first dose of study drug and
 - o The AE was not present prior to first dose of study drug
 - o An AE was present prior to first dose of study drug:
 - The same AE (based on preferred term) started 2 or more days after the end date of the AE present prior to first dose
 - The same AE (based on preferred term) starts at the end date or the day after the end date of the AE present prior to the first dose and new AE has worsened, ie an increase in toxicity grade or changed to an SAE
- The start date of the AE is missing
- The start time of the AE is missing, and the AE was not present the day before first dose of study drug, and the start date of the AE is the same as the start date of first dose of study drug
- The day is missing of the AE start date but month and year are the same as month and year of first dose of study drug
- The month is missing of the AE start date but year is the same as year of first dose of study drug

Phase allocation of AE

Adverse events present in the SDTM database are allocated to phases based on their start date and time. If the start date and time of an event falls between (or on) the start and stop date and time of a phase, the AE is attributed to that phase (treatment-emergent principle).

Rule: phase start datetime \leq AE start datetime \leq phase stop datetime.

Incomplete AE dates and or times (ie, time and/or day and/or month and/or year missing):

- In case of partial AE start dates and or times, the events are allocated to the phases using the available partial information on start and end datetime; no imputation will be done. If, for instance, for the AE start date only month and year are available, these data are compared to the month and year information of the phases. This rule may lead to multiplication of the event as a consequence of its assignment to multiple phases.
- In case of a completely missing AE start date, the event is allocated to the first active treatment phase, except if the end date of the AE falls before the start of this active treatment phase.
- In case of a completely missing AE end date, the following rules apply:
 - in case the date is identified as unknown the date will remain missing;
 - in case the date is not flagged as unknown the date is assumed to be the cut-off date of the analysis for subjects still ongoing in the study, and the end date of the last phase for subjects who discontinue or completed the study.

Examples:

Screening phase: start date: 02JAN2017 - stop date: 28JAN2017

Treatment phase: start date: 29JAN2017 - stop date: 12AUG2017

1) Adverse event: start date: JAN2017- stop date: 15JUL2017

As the AE start date only has information about month and year, only this information will be used from the phases and therefore the AE will be assigned to the screening phase as well as to the treatment phase.

2) Adverse event: start date: JAN2017- stop date 27JAN2017 As the AE stops before or at the start of the treatment phase, it is only assigned to the Screening phase.

Remarks: In addition to the date information, time information is taken into account to allocate AEs to phases.

Adverse events

The variables attributed to adverse events are

- AE term (verbatim and MedDRA preferred term and system organ class)
- Onset datetime, End datetime and duration of AE
- Serious AE (Yes/No), if yes classification will be listed
- Toxicity grade (Mild, Moderate, Severe, Potentially life-threatening)
- Action taken with study treatment (Dose not changed, Dose interrupted, Drug withdrawn, Not applicable, Unknown)
- Relation to study treatment (Not related, Doubtful, Possible, Probable, Very likely)
- Outcome of AE
- AE leading to death (Yes/No)
- Concomitant treatment taken for AE (Yes/No)

- Influenza-related complication (Yes/No)
- Required hospitalization/prolonged hospitalization (Yes/No)

Anticipated Events

An anticipated event is an AE (serious or non-serious) that commonly occurs as a consequence of the underlying disease or condition under investigation (disease related) or background regimen.

For the purposes of this study the following events will be considered anticipated events. (see [Attachment 1](#) for the classification of AEs into Anticipated Events and Anticipated Event Groups):

- Pneumonia
- Bronchitis
- Sinus infections
- Ear infections
- Worsening of asthma, asthma attack
- COPD exacerbation
- Complications of sickle cell disease, sickle cell crisis
- Complications of diabetes mellitus, diabetic ketoacidosis
- Acute respiratory distress syndrome (ARDS)

Influenza-related complications

The categories of influenza-related complications are defined in the efficacy Section [5.3.1.3](#).

Note: the investigator's categorization and assessment of complications may be overruled by the Adjudication Committee.

Confirmed diarrhea events

Additional details required to confirm a diarrhea event, including number of loose stools episodes per day and stool consistency, will be collected for subjects who report a diarrhea type event.

A confirmed diarrhea event is defined as three or more loose stools episodes per day with a consistency of 'loose' or 'watery'.

7.1.2. Analysis Methods

Treatment-emergent adverse events

There will be no formal statistical testing unless indicated otherwise.

A summary will be provided for the following TEAEs per phase (Treatment phase, Follow-up phase) and for the combination of Treatment and Follow-up phases:

- any adverse events,
- serious adverse events,
- deaths due to AE,
- adverse events by worst toxicity grade,
- AEs of worst grade 3 or 4
- AEs of worst grade 3

- AEs of worst grade 4
- AEs at least possibly related to study drug,
- AEs for which study drug was temporarily stopped,
- AEs for which study drug was permanently stopped,
- AEs leading to study discontinuation
- serious adverse events that were at least possibly related to study drug.
- adjudicated influenza related complications
- COVID-19 AEs
- COVID-19 serious adverse events
- COVID-19 non-serious adverse events

The adverse events will be shown by MedDRA system organ class and preferred term, in order of descending frequency in the pimodivir group. For each AE, the percentage of subjects who experience at least 1 occurrence of the given event will be summarized by treatment group and per phase (Treatment phase, Follow-up phase) and for the combination of Treatment and Follow-up phases. Incidence tabulations will be provided for the following categories:

- any adverse events
- serious adverse events
- AEs at least possibly related to study drug
- AEs for which study drug was temporarily stopped
- AEs for which study drug was permanently stopped
- AEs leading to study discontinuation
- serious adverse events that were at least possibly related to study drug
- AEs related to COVID-19 infection
- Serious adverse events related to COVID-19 infection
- AEs related to COVID-19 infection leading to death

and in addition for treatment emergent adverse events with incidence of at least 5% in any treatment group.

In order to fulfil requirements for the plain language summary document and presentations for EudraCT the following adverse event categories will be shown by MedDRA system organ class and preferred term per phase (Treatment phase, Follow-up phase) and for the combination of Treatment and Follow-up phases. No tabulations by subgroups will be provided for these categories:

- deaths due to AEs that were at least possibly related to study drug
- AEs for which study drug was permanently stopped that were at least possibly related to study drug

- non-serious AEs that were at least possibly related to study drug
- any non-serious AEs

AEs leading to death, SAEs, AEs leading to dose interruption or permanent stop of study drug, AEs related to COVID-19 infection will be listed separately. All AEs will be listed in an individual subject data listing, including pre-treatment AEs. All listings will be provided for the safety set.

The duration (in days) of an AE is calculated based on the AE start date and AE end date as:

$$\text{AE duration} = \text{AE end date} - \text{AE start date} + 1$$

Note that the AE duration will only be calculated when the start date and end date is fully known, in case of partial or missing start and end dates the AE duration will be missing.

Anticipated Events

Frequency tabulations of anticipated events and anticipated event grouped terms will be shown for treatment phase, follow-up phase and for the combination of treatment and follow-up phases. The tabulation will show per treatment the number (%) of subjects with serious, non-serious and total anticipated events and anticipated event grouped terms and a one-sided p-value of Fisher exact test for anticipated events and anticipated event grouped terms. Note that the Fisher exact test will only be provided for the occurrence of events for the combination of treatment and follow-up phases.

A listing of the anticipated events will be added.

More details on the anticipated events analysis can be found in the Anticipated Events Safety Monitoring plan.

Influenza-related complications

Adverse Events adjudicated as influenza-related complications will be tabulated by category and adverse event, for treatment phase and follow-up phase and for the combination of treatment and follow-up phases.

Adverse events investigator-assessed as influenza-related complications will also be tabulated by category and adverse event, for treatment phase and follow-up phase and for the combination of treatment and follow-up phases. A listing showing the AEs reported as influenza-related complications and complication information will be made linking the information to the AE listing.

Confirmed diarrhea events

The number and percentage of subjects who experience at least 1 occurrence of confirmed diarrhea events will be summarized by treatment group and per phase (Treatment phase, Follow-up phase) and for the combination of Treatment and Follow-up phases.

For all subjects that complete the additional diarrhea form, a cross-tabulation of number of loose stools episodes per day (categorized as 1, 2, 3 or more) versus stool consistency will be produced by treatment group and per phase (Treatment phase, Follow-up phase) and for the combination of

Treatment and Follow-up phases. If a subject has more than 1 diarrhea event per phase, then the worst response from all events in that phase will be tabulated.

Descriptive statistics will be produced by treatment group for the number of days from first dose of study drug to onset of first diarrhea event and for total duration of diarrhea events. A frequency tabulation will be produced by treatment group for the number of days from last dose of study drug to resolution of last diarrhea event.

Frequency tabulations will be produced by treatment group and per phase (Treatment phase, Follow-up phase) and for the combination of Treatment and Follow-up phases for the severity grade of the diarrhea event and for whether any concomitant medication was used to treat the diarrhea event.

No tabulations by subgroups will be provided.

All information recorded on the specific diarrhea form will be listed.

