##### **Adverse drug reactions:**

A formal adverse drug reaction (ADR) identification process was conducted on the clinical safety data of Study 63623872FLZ2001 and Study 63623872FLZ2002. No serious ADRs have been identified to date. Diarrhea is considered a non-serious ADR because most cases were mild or moderate.

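### Diarrhea still unresolved at last contact has no defined place in the SAP's duration and days-to-resolution tables, so both tend to describe only events that ended

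*SAP*

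**What the plan says.** **Duration rule.** SAP Section 7.1.2 computes AE duration as end date minus start date plus one day. It then states that "the AE duration will only be calculated when the start date and end date is fully known" and that "in case of partial or missing start and end dates the AE duration will be missing".

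**Outputs that depend on it.** Under the confirmed-diarrhea heading, the same section plans descriptive statistics by treatment group for total duration of diarrhea, and a frequency table of "the number of days from last dose of study drug to resolution of last diarrhea event". It gives no censoring rule, no category for events that have not resolved and no count of events left out.

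**A second rule for missing end dates.** SAP Section 7.1.1, in the text on allocating AEs to phases, says of a completely missing end date that "in case the date is identified as unknown the date will remain missing". Otherwise, "in case the date is not flagged as unknown the date is assumed to be the cut-off date of the analysis" applies to subjects still in the study, "and the end date of the last phase for subjects who discontinue or completed the study". Section 7.1.2 does not mention this assumed date.

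**Status of diarrhea.** Protocol Section 1.4.3 names one adverse drug reaction: "Diarrhea is considered a non-serious ADR because most cases were mild or moderate". The SAP amendment history shows that the diarrhea tables were added in Amendment 2 and the duration derivation in Amendment 3.

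**The concern.** An event that is still open has no known end date. If such events are dropped, the duration table is conditional on the event having ended, and long events are the likelier ones to be still open at last contact. The resolution table has the same limit, because an unresolved event has no resolution day to tabulate.

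The SAP treats the same data problem differently for efficacy. Unresolved influenza symptoms (Section 5.2.1) and unresolved fever (Section 5.3.1.3) are censored and summarized by Kaplan-Meier (Section 5.3.2). At stake is how long the drug's one named adverse reaction is reported to last. It is also possible for two programmers following the SAP to produce different tables.

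**Working it through.** **Step 1. The two rules side by side.** The plan states no figure on this point, so the check starts with the text.

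| State of the end date | Section 7.1.1 | Section 7.1.2, read literally |
|---|---|---|
| Fully known | no rule needed | duration calculated |
| Partial | no imputation | missing |
| Completely missing, flagged unknown | stays missing | missing |
| Completely missing, not flagged | assumed date (cut-off or end of last phase) | missing, unless the assumed date counts as known |

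Only the last row is open to two readings. If the assumed date is not used, the open event drops out. If it is used, the event enters as though it had ended with the last phase, so a lower bound is reported as a completed duration. Neither reading shows the event as unresolved.

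The SAP also does not say how a subject's total is formed when one of several events has no duration. Whether the subject contributes only the ended events or nothing at all, the open event's days are not counted.

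**Step 2. Illustrative size.** Let f be the share of diarrhea events unresolved at last contact, m the mean duration of resolved events, and d the days from onset to last contact for open ones. The documents give none of the three, so all values here are assumptions. The choice d = 24 is onset on Day 5 and still open on Day 28 (28 − 5 + 1 = 24).

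- Reported mean with open events dropped: m
- Mean with open events kept at d, itself a lower bound: (1 − f)·m + f·d
- Understatement: 1 − m / [(1 − f)·m + f·d]

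| m | f | (1 − f)·m + f·24 | Reported mean too low by |
|---|---|---|---|
| 3 | 0% | 3.00 | 0% |
| 3 | 2% | 2.94 + 0.48 = 3.42 | 12.3% |
| 3 | 5% | 2.85 + 1.20 = 4.05 | 25.9% |
| 3 | 10% | 2.70 + 2.40 = 5.10 | 41.2% |
| 5 | 2% | 4.90 + 0.48 = 5.38 | 7.1% |
| 5 | 5% | 4.75 + 1.20 = 5.95 | 16.0% |
| 5 | 10% | 4.50 + 2.40 = 6.90 | 27.5% |

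Varying d from 14 to 28 days over the same m, with f from 2% to 10%, widens the range to about 3.5% to 45%.

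**Step 3. The median.** If every open event outlasts the reported median, that median is the (1 − f)/2 quantile of all events. This is the 49th percentile at f = 2% and the 45th at f = 10%. The median barely moves; the mean and the upper end of the distribution carry the effect.

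**Step 4. Does the arm matter?** Protocol Section 1.1 gives community-study diarrhea rates of 27.0% on 600 mg bid alone, 17.8% with oseltamivir and 5.6% on placebo. With 360 per arm these are 0.270 × 360 ≈ 97, 0.178 × 360 ≈ 64 and 0.056 × 360 ≈ 20 subjects. At an assumed common f of 5%, about 97 × 0.05 ≈ 4.9 subjects' events are hidden against 20 × 0.05 = 1.0. The formula in Step 2 depends on f and not on these counts, so with the same m and d the understatement of the mean is identical in both arms.

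**The case against.** The strongest reply is that the problem is small and partly covered. Dosing lasts 5 days and follow-up runs to Day 28. Protocol Section 9.6.1 has persisting events followed beyond the end of the study, so many end dates should be obtained, and Protocol Section 1.1 describes the hospital-study diarrhea as transient. An event that begins late and is still open need not be long. AE outcome is a recorded variable, all AEs are listed and the diarrhea form is listed in full. Table shells are kept in a separate document (SAP Section 1) and may contain an unresolved row. The outputs are descriptive and carry no formal test.

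Most of this stands as an argument about size. It does not remove the gap. Section 9.6.1 also lets follow-up stop at a stable but unresolved state, and subjects lost to follow-up can leave with an event open. Listings do not correct a summary table. The SAP text, which is what fixes the derivation, names neither a censoring rule nor an unresolved category.

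The assumed end date in Section 7.1.1 is a fair point against saying that every ongoing event certainly drops out. It does not settle the matter: it sits under phase allocation, leaves dates flagged unknown as missing, and would present an open event as completed.

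**Conclusion.** The point holds for two tables: total diarrhea duration and days from last dose to resolution. As written they tend to describe resolved events only, and so to understate duration. The direction rests on reading Section 7.1.2 literally and on open events generally being longer than resolved ones. The size cannot be derived from the documents. It is zero if no event is open at last contact and probably modest otherwise; the percentages above are illustrations.

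Stronger readings that a reader might infer are not supported:

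- **That the bias falls mainly on pimodivir.** More diarrhea means more hidden events, but the bias in an arm's mean depends on its unresolved share, and nothing in the documents shows that this share differs by arm.
- **That the adverse reaction as a whole is understated.** Incidence, severity grade, stool count and consistency, days to onset and treatment of the event do not use the duration rule.
- **That Section 7.1.1 also causes days to be counted twice.** Its rule on an event starting on another's end date concerns an event present before first dose.
- **That the stools-by-consistency table inflates confirmed diarrhea.** Confirmation is defined per event and counted separately.

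**What to change.** In SAP Section 7.1.2:

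1. State that the end date assumed in Section 7.1.1 is not used as a completed duration.
2. For the diarrhea tables, summarize duration with unresolved events censored at last contact, for example with a Kaplan-Meier median. State whether this applies per event or to the subject's total; for a total, treat it as censored if an event in it is still open. At minimum, report by arm the number of events excluded as unresolved.
3. Add a row for events not resolved at last contact to the days-to-resolution table.

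The cost is a few lines of SAP text and minor programming. No new data are needed. The reported duration may become slightly longer. With a small unresolved share the median will hardly change, so the count by arm is the most informative addition.
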